##### *9.5.5.2 Study Treatment Accountability*

All supplies of study medication and placebo will be accounted for in accordance with GCP. There will be an individual study drug accountability record for each subject and the Investigator will maintain accurate records of the disposition of all study medication supplies received during the study. These records will include the amounts and dates clinical drug supplies were received and then dispensed to the subject, and unused supplies returned by the

subject to the Sponsor. If errors or damages in the clinical drug supply shipments occur, the Investigator will contact the study monitor and the Sponsor immediately. Copies of the study medication accountability records will be provided by each Investigator for inclusion in the Trial Master File after database lock. The study monitor will periodically check the supplies of study medication held by the Investigator or pharmacist to verify accountability of all medication used.

The Investigator will dispense the medication only to the identified subjects in this study, according to the procedures described in this study protocol. After the end of the study, all unused medication and all medication containers will be returned to Spyryx Biosciences, Inc. or its designee for destruction. The Sponsor will verify that a final report of drug accountability is prepared and maintained in the Investigator's Study Center File.

### **9.5.6 Dose Adjustments and Dose Escalation**

Not applicable to this study

### **9.5.7 Prior and Concomitant Therapy**

Any treatment not explicitly excluded and considered necessary for the subject's welfare may be given during the study at the discretion of the Investigator. Administration of concomitant medications must be reported in the appropriate eCRF with dosage information, dates of administration, and reasons for use. Generic names for concomitant medication should be used if possible. The total daily dose should be filled in whenever possible.

Randomization (Day 1) and initiation of study drug should be scheduled to coincide with the first day of a cycle of inhaled antibiotics, if applicable. If simultaneous initiation of the study drug and inhaled antibiotics cannot be accommodated, the subject may be randomized, provided they start their 28-day cycle within  $\pm$  3 days of Visit 2.

In general, the subject's usual routine of medication and chest physiotherapy are to be continued unchanged throughout the study. The study drug should be added into the subject's treatment regimen as the last mucolytic therapy inhaled (ie, after inhalation of dornase alfa, mannitol, and/or hypertonic saline) but before the inhalation of antibiotics or corticosteroids. The only exception to this rule is on the mornings of all clinic visits. The following procedures should be followed on clinic days only:

- If a long-acting  $\beta$ -agonist (LABA) is taken regularly in the morning, instruct the subject to take it the evening prior to all clinic visits and not take it the morning until after all clinic assessments have been completed.
- If a short-acting  $\beta$ -agonist (SABA) is taken regularly, the subject should ensure that it is taken at least 4 hours before the clinic visit.
- The subject should be instructed not to take the morning dose of the study drug, but they should complete the regular routine of medications and chest physiotherapy at home (including inhaled antibiotics); the study drug will be administered during the clinic visit.

#### *9.5.7.1 Prohibited Medications*

Use of the following antihypertensive medications or combinations containing them is

prohibited within 28 days before screening and during the study:

- Diuretics (eg, thiazides, loop diuretics, spironolactone, and amiloride)
- Angiotensin-converting enzyme inhibitors
- Angiotensin receptor blockers
- Any other drugs known to affect the serum potassium concentration

#### **9.5.8 Treatment Compliance**

It is the Investigator's responsibility to ensure that subjects are correctly instructed about how to take their study medication and use the PARI eFlow nebulizer with PARI eTrack, and understand the importance of being compliant with their assigned dose regimen. Records of study medication used and intervals between visits will be kept during the study. Drug accountability will be noted by the study monitor during site visits and at the completion of the study. Subjects will be asked to return all unused medication at the end of the study. Subjects should be instructed to discard used medication vials at home as the vials are used, to reduce the risk of infection. The study treatment should be dispensed by the Investigator, or by a qualified individual under the Investigator's supervision. The Investigator must maintain an up-to-date treatment inventory and dispensing record (see [Section 9.5.5.2](#)).

At each visit, the Investigator will collect previously dispensed, unused study medication and assess compliance. Subjects exhibiting poor compliance should be counseled on the importance of complying with study procedures. Subjects who are persistently noncompliant may be withdrawn from the study but only after consultation with the Medical Monitor.

Where available, study drug compliance will be assessed electronically via a Bluetooth accessory called eTrack on the PARI eFlow investigational nebulizer. This monitor will capture the date and time of use of the investigational nebulizer. Subjects will be made aware of this feature and provided with the equipment and instructions to set this up for use in their home. Study coordinators will be expected to monitor study drug usage and intervene via phone call, etc. if there are any obvious problems (such as using the nebulizer too much, too little, etc).

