#### **13.6.6 Safety**

Safety data will be summarized for the safety population.

Exposure to the study drug will be summarized. Summaries will include the number of doses received and dose compliance.

All AEs reported after initiation of treatment, and pre-existing conditions that worsen or become more frequent after initiation of treatment will be considered TEAEs. Adverse events will be coded by system order class and preferred term using MedDRA. All recorded AEs will be included in the data listings.

The number and percentage of subjects with TEAEs, SAEs, AEs leading to death, and AEs leading to discontinuation of the study drug will be summarized by preferred term, and where appropriate, system organ class. Deaths, SAEs, and AEs leading to discontinuation of the study drug will also be listed, and narratives will be written.

Summary statistics for actual values and for change from baseline will be tabulated as appropriate for vital signs and clinical laboratory test results. Results of ECGs will be summarized and results of physical examinations will be listed.

All non-study medications received during the treatment period will be considered concomitant medications. Previous and concomitant medications will be coded using the WHO Drug Dictionary and will be summarized.

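### Protocol Section 9.5.8 lets randomized subjects be withdrawn from the study for undefined persistent non-compliance, which can remove them from the primary Week 4 analysis

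*Protocol*

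**What the plan says.** **Withdrawal.** Protocol Section 9.5.8 first provides for counselling: "Subjects exhibiting poor compliance should be counseled on the importance of complying with study procedures". It then adds: "Subjects who are persistently noncompliant may be withdrawn from the study but only after consultation with the Medical Monitor". It does not define persistence, and the Medical Monitor is to be consulted, not to approve. Section 9.4.4.1 lists a subject's unwillingness to continue as a separate withdrawal reason. It does not name non-compliance, although its general investigator-decision reason could cover it.

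**Analysis.** The ITT set is all randomized subjects, grouped as randomized whatever they actually received (Protocol Section 13.5.2, SAP Section 9.1), and SAP Section 9.1 makes it the primary efficacy population. SAP Section 8.0 (Change from Baseline) leaves subjects with a missing change out of the analysis of that change, and SAP Section 12.6.1 imputes nothing in the primary ANCOVA. Withdrawn subjects are not replaced (Protocol Section 9.4.4.4).

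**Measuring compliance.** Section 9.5.8: "At each visit, the Investigator will collect previously dispensed, unused study medication and assess compliance". The same section says: "Subjects should be instructed to discard used medication vials at home as the vials are used, to reduce the risk of infection". Section 9.5.5.2 says that after the study "all unused medication and all medication containers will be returned". Electronic monitoring is conditional: "Where available, study drug compliance will be assessed electronically via a Bluetooth accessory called eTrack on the PARI eFlow investigational nebulizer". For reporting, Protocol Section 13.6.6 promises: "Summaries will include the number of doses received and dose compliance". SAP Section 12.4 plans no summary of exposure or compliance and no transfer of the nebulizer data.

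**The concern.** An ITT comparison is meant to include poor compliers. The sentence in Section 9.5.8 permits ending a subject's study participation because of behaviour seen after randomization, even if that subject would still attend visits. When the primary analysis is complete-case, ending participation before Week 4 usually means losing the subject from the comparison. If adherence is related to treatment arm or to outcome, those who remain are no longer the groups that randomization formed, and the estimate moves toward the effect in good compliers. The change-from-baseline CFQ-R endpoint is lost for every early terminator, because Protocol Section 10.6 omits that questionnaire for them.

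The compliance measure matters less, but it feeds the decision. With empties thrown away, a vial that is not handed back looks the same as a vial that was used.

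**Working it through.** **1. From withdrawal to the primary analysis**

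- A withdrawn subject has an early termination visit as soon as possible, and at the latest 14 days after withdrawal or stopping treatment (Protocol Section 9.4.4.2).
- SAP Section 8.0 (Analysis Visit window) assigns Study Days 12 to 21 to Week 2 and Day 22 onward to Week 4.
- Example: withdrawal on Day 15, with the visit due by Day 15 + 14 = Day 29. If the visit is held before Day 22, the subject has no Week 4 value. If it is held on Day 22 or later, the subject has one, possibly measured off drug.
- So loss of the primary endpoint is likely after a prompt early visit, but not certain.

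**2. The plan's power figure**

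Inputs (Protocol Section 13.2): 45 subjects at 2:1 (30 versus 15), SD 7.58, one-sided alpha 0.1, differences of 6 and 8. Standard error = 7.58 × √(1/30 + 1/15) = 2.40. Noncentral t power with 43 degrees of freedom is 88.4% and 97.8%, which agrees with the stated 88% to 97%.

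For scale, all-cause non-completion in Cohort 1 was 5/45 treated = 11.1%, or 6/46 randomized = 13.0% (40 completers, Protocol Section 7.3.2). Losing Week 4 values at that rate gives:

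| Analysed | Power at 6 | Power at 8 |
|---|---|---|
| 45 (30 vs 15) | 88.4% | 97.8% |
| 40 (27 vs 13) | 85.0% | 96.5% |
| 39 (26 vs 13) | 84.7% | 96.3% |

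That costs 3 to 4 points at a difference of 6, and it counts losses for every reason. Power is not the main issue; selection is.

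**3. Size of the selection effect (illustration)**

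Assume that k of the 30 active subjects under-dose and gain nothing, the others gain 6 points, and the k have no Week 4 value. Neither k nor the zero gain is given in the documents.

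- Effect in all randomized subjects = 6 × (30 − k)/30. Effect after removal = 6. Overstatement = k/(30 − k).
- k = 1: 5.8 points, overstated by 3.4%. k = 2: 5.6 points, 7.1%. k = 3: 5.4 points, 11.1%.
- If one of three such subjects keeps a Week 4 value, the estimate is 6 × 27/28 = 5.79. Against 5.4 that is 7.1%.
- The largest absolute shift here is 6.0 − 5.4 = 0.6 points, a quarter of the 2.40 standard error.

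If the drug is inert and three active subjects who fall by 4 to 6 points are removed, the estimate rises by 3 × 4/30 = 0.4 to 3 × 6/30 = 0.6 points. Removing one of 15 placebo subjects with the same fall takes back 4/15 = 0.27 to 6/15 = 0.40, leaving 0.13 to 0.20. Losses on placebo therefore offset the part that comes from poor compliers doing worse in either arm.

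**4. What the vial count can show**

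Inputs: 4 vials a day (Protocol Table 4); an 8-day box for each of the first two intervals and two boxes for the last (Section 10.2.3).

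- One box is 32 vials. Over 7 days a full complier uses 28 and returns 4. At 80% intake 22.4 are used and 9.6 come back. At 50% intake 18 come back. Returned vials do reveal missed doses.
- In total 4 × 32 = 128 vials are dispensed against 28 × 4 = 112 needed. A subject who returns none is credited with 128/112 = 114% at any true intake.
- At 80% intake 89.6 are used and 38.4 are left. If half the leftovers (19.2) come back, the credit is (128 − 19.2)/112 = 97%.
- The count is therefore an upper bound on doses taken, and it is accurate only if all leftovers are returned.

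**The case against.** The safeguards are real. Counselling comes first, withdrawal is optional and reserved for persistent cases, and the Medical Monitor must be consulted. Clinic compliance checks fall on about Days 8 and 15, so persistence may not be established before Day 15, and some early termination visits will then fall in the Week 4 window. In Cohort 2, MMRM and multiple imputation both cover the ITT set. All of this limits the likely number of lost values. It does not remove the permission, and both supportive models predict the missing value from observed data where an actual measurement could have been taken.

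A reader might infer more than the documents support:

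- *That the vial count cannot show non-compliance.* It can, as step 4 shows. A count that overstates compliance would also trigger fewer withdrawals, not more.
- *That withdrawn subjects leave the ITT population.* They do not. The loss comes through the missing-data rules.
- *That the bias is large and tied to arm.* An overstatement of 25% would need 6 of 30 active subjects removed for non-compliance alone (6/24), above the 11% to 13% all-cause non-completion in Cohort 1. Cough at 120 mg, the only Cohort 2 dose, was 6.3% against 0% on placebo; the 26.7% figure belongs to the 60 mg arm (Protocol Table 1). A link to arm is possible but not shown.
- *That the vial instructions certainly contradict each other.* Section 9.5.3 calls the outer packaging the container for the vials, so Section 9.5.5.2 may mean boxes. The wording needs clarifying either way.

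**Conclusion.** The point holds in a limited form. Section 9.5.8 permits study withdrawal for undefined persistent non-compliance without the subject wishing to leave, and the visit windows and complete-case rule can turn that into loss from the primary analysis. This works against an ITT comparison intended to ignore treatment actually received.

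The size is unknown. The 3% to 11% range rests on an assumed 1 to 3 of 30 active subjects, no benefit in them and no Week 4 value. It would be smaller if some had a value on Day 22 or later, and losses on placebo could offset any prognostic part. The rule brings no analytic gain, because the Per-Protocol set (Protocol Section 13.5.3, SAP Section 9.2) already allows a supportive analysis without major violators. The change is worth making because it is cheap, not because a large bias has been shown.

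Two secondary points stand as inconsistencies: used vials discarded versus all containers returned, and compliance summaries required by the protocol but absent from the SAP.

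**What to change.** 1. Amend the sentence in Protocol Section 9.5.8 so that low compliance alone does not end study follow-up, and subjects willing to attend complete the remaining visits, including Visit 5 (Day 29) spirometry. Leave decisions on stopping study drug and on safety withdrawal as they are.
2. Reconcile Sections 9.5.8 and 9.5.5.2 on whether used vials are discarded or returned. If empties are not available, label any compliance figure based on returned vials as an upper bound.
3. Reconcile Protocol Section 13.6.6 with SAP Section 12.4: either plan the summary of doses and compliance, or record its omission under SAP Section 4.1 (Changes from Protocol).

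The first change costs one sentence and a few more visits. Its downside is that a few poor compliers stay in the primary analysis and the estimate may be slightly smaller. Using eTrack data for the third would cost more than wording, because the SAP intends no data transfer and files the adherence report only as a PDF, so the data would have to be transferred or extracted.

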#### **9.5.9 Assignment to Treatment**

The Investigator or designee will use IXRS to randomize eligible subjects. Randomization for Cohort 1 was stratified by the Visit 2 pre-dose ppFEV1 (between 40.0% and 55.0% vs between 55.1% and 80.0%). Randomization for Cohort 2 will be stratified by use of concomitant hypertonic saline (defined as having used a constant regimen for 28 days prior to screening and planning to continue with no change through 28 days post-randomization), so that approximately 50% of subjects will be using hypertonic saline. Only those subjects who have met the randomization criteria ([Section 9.4.3](#)) will be eligible for assignment to study treatment. Subjects who fail to meet the randomization criteria may have Visit 2 repeated once, or they will be considered a screen failures.

#### **9.5.10 Unblinding Procedures**

Within the IXRS system, the Investigator may break the blind by clicking on the "Break Blind" button. The Investigator will then be prompted to enter either the Kit ID number or

Subject ID number and select “next.” The Investigator will then be prompted to confirm the blind should be broken. After selecting “Yes,” the Investigator will be prompted to enter a reason for breaking the blind. Once a reason has been properly entered, a warning will appear and once again the Investigator will select “confirm” and then will be prompted to enter the appropriate IXRS user password. The Investigator will then confirm this selection and the subject information with the unblinding data will be displayed. Additional procedures for unblinding in case of emergency will be detailed in the IXRS manual. See Appendix 5 ([Section 18.5](#)) for more details.

## **9.6 Efficacy and Safety Variables**

### **9.6.1 Efficacy and Safety Measurements Assessed**

#### *9.6.1.1 Efficacy Variables*

- Primary
  - Change from baseline in ppFEV1 at Week 4
- Secondary
  - Change from baseline in ppFEV1 at other visits
  - Change from baseline in FEV1
  - Change from baseline in FVC and ppFVC
  - Change from baseline in CFQ-R

#### *9.6.1.2 Safety Variables*

- Incidence of treatment-emergent AEs
- Changes in vital signs
- Changes in clinical laboratory tests, including urine and blood electrolytes
- Changes in ECGs

#### *9.6.1.3 Pharmacokinetic Variable (Cohort 1 Only)*

- Systemic exposure to SPX-101 (subset of subjects)

#### *9.6.1.4 Exploratory Variables*

- Incidence of pulmonary exacerbation, as defined by Fuchs [[4](#)] (See Appendix 3, [Section 18.3](#) for details)
- Incidence of antidrug antibodies (ADA)

## **10. STUDY EVALUATIONS BY VISIT**

### **10.1 Visit 1: Screening (Day -28 to -3)**

There is a variable-length screening period of 3 to 28 days to the time of randomization so that the first dose of the study drug coincides, if applicable, to the first day of an inhaled antibiotic cycle. Additional information can be found in [Section 9.5.7](#).

At the Screening Visit, the following assessments/procedures will be performed in approximately the following general order:

- Informed consent
- Medical history
- Previous and concomitant medications
- Vital signs
- Height, weight, BMI
- Complete physical examination
- Spirometry
- 12-lead ECG
- Blood samples collected for hematology and serum chemistry tests and serum pregnancy test
- Assessment of eligibility

Note: Subjects may be re-tested once within 7 days to complete their eligibility assessments.

### **10.2 Visit 2: Day 1 (Randomization)**

#### **10.2.1 Pre-Randomization Assessment**

- CFQ-R
- AE assessment
- Concomitant medications
- Pre-dose spirometry
- Urine collected for urinalysis, urine electrolytes, and urine pregnancy
- Vital signs
- Abbreviated physical examination
- Weight and BMI
- 12-lead ECG
- Blood collected for hematology and serum chemistry tests, including electrolytes and pre-dose sample for PK (Cohort 1 only)
- Review randomization criteria to ensure eligibility

Note: A subject may be re-screened once if they fail to meet the Randomization criteria for any reason. If this is the case, a new consent form must be signed, and a new screening number will be used.

#### **10.2.2 Randomization and Study Procedures**

- Randomization using IXRS

- The Investigator or designee will issue the eTrack study nebulizer and will train subjects on its use and all study procedures, and will review all instructional materials and ensure subjects understand all procedures and instructions
- Study medication administration and postdose monitoring for at least 4 hours after completion of administration
  - Blood for PK analysis will be collected at  $5 \pm 2$  minutes and  $15 \pm 3$  minutes after completion of administration of the study drug (Cohort 1 only)
  - Post-dose spirometry at  $30 (\pm 15)$  minutes, 2 hours ( $\pm 15$  minutes), and 4 hours ( $\pm 15$  minutes) after completion of administration of the study drug
  - Vital signs at  $30 (\pm 15)$  minutes, 1 hour ( $\pm 15$  minutes), 2 hours ( $\pm 15$  minutes), and 4 hours ( $\pm 15$  minutes) after completion of administration of the study drug
- Dispense study medication, nebulizer, and baby bottle sterilizer
- Schedule the subject's next visit and review instructions (See Appendix 4, [Section 18.4](#))

If the subject experiences symptoms of acute bronchospasm following the first dose of study medication, the subject should be treated with SABAs or other treatment at the discretion of the Investigator and continued to be observed for at least 2 hours post-SABA or the 4-hour postdose timepoint, whichever is longer. If the subject's bronchospasm has been relieved and the subject is stable for at least 30 minutes at the 2-hour post-SABA or 4-hour postdose timepoint, the subject may continue in the trial at the discretion of the Investigator. If medically essential, the Investigator may elect to require that the subject be pre-treated with a SABA or other medication before every subsequent dose, or the PI may withdraw the subject from the study. If the subject requires pre-treatment with a SABA or other medication for subsequent doses, this drug will be recorded as a concomitant medication, and the bronchospasm will be reported as an AE. Additional follow-up procedures may be instituted at the discretion of the Investigator.

#### **10.2.3 Post-Randomization Visit Schedule**

Randomized subjects will return to the clinic after approximately 1, 2, and 4 weeks of treatment. Study drug consisting of an 8-day supply will be dispensed weekly to cover the period from Visit 2 to Visit 3 and again from Visit 3 to Visit 4. At Visit 4, a 2-week supply (2 boxes with an 8-day supply in each) will be dispensed to cover the period from Visit 4 to Visit 5. Sites must schedule subjects for Visit 3, 4, and 5 within the provided visit windows taking into account drug supply.

#### **10.3 Visit 3: Day 8 (-1 Day)**

- Concomitant medications
- AE assessment
- Vital signs
- Abbreviated physical examination
- Pre-dose spirometry
- Urine and blood samples collected for electrolytes

- Study drug administration
- Dispense study drug
- Collect unused study drug from previous visit
- Schedule the subject's next clinic visit and review instructions (Appendix 4, [Section 18.4](#))

